1. OBJECTIVES

1.1 Study Design

The objective of this non-randomized, open label study is to evaluate the safety and efficacy of an intraoperative imaging system, the LUM Imaging System (LUM015 in conjunction with imaging device LUM 2.6), in identifying residual cancer in the tumor bed of female breast cancer subjects. The study is composed of a Feasibility Trial divided into Phase A (up to 15 total subjects, completed as of December 4, 2015) and Phase B (up to 50 total subjects). Phase A included 5 subjects not injected with LUM015 for autofluorescence tissue assessment and 10 subjects receiving LUM015 (as outlined below) to assess the ability to distinguish LUM015 from autofluorescence. Phase A concluded with the analysis of the data to (1) assess patient safety, (2) determine the parameters of the detection algorithm, (3) select the dose for Phase B and (4) evaluate the device function. These results were reported to FDA prior to starting the Phase B part of this study. In Phase A, no adverse events related to the investigational product were reported (n=15 patients). Luminicell also determined the tumor detection threshold parameters based on comparison of imaging data with pathology results. The dose selected for Phase B is 1.0 mg/kg based on Luminicell's dose-response model and Phase A data. During Phase B, we will preliminarily assess the performance of the detection algorithm and adjust the threshold parameters if needed.

Nomenclature:

Throughout this protocol, reference is made to the orientation of the lumpectomy cavity (tumor bed) and the shaved margins specimens. When a lumpectomy is performed, there are typically 6 surfaces defined as if the cavity is a cube. To determine the margin status (either positive or negative), a cavity shaving is taken from each surface of the tumor bed and analyzed by a pathologist. Note that there will be no intraoperative frozen section analysis of the gross resection or shavings during this study because frozen section analysis is not standard of care for breast cancer surgeries. **Figure 1** shows a schematic representation of the nomenclature for the lumpectomy cavity margins, showing 5 locations. The sixth surface (not shown in the figure) is the “anterior” margin which is the margin nearest to the skin which could blend into one or more of the side surfaces depending on how the initial incision is done. Typically, a shaved margin specimen is not taken from the posterior surface if the lumpectomy cavity reaches the fascia over the pectoral muscle. Thus, in a given lumpectomy, there will be between 4 to 6 shaved margin specimens.

Margins will be assessed per standard of care by a pathologist by measuring the distance to the inked surface of each tissue shaving from invasive cancer or ductal carcinoma in situ (DCIS). In this study, a positive margin is defined as invasive cancer or DCIS present on the inked surface.

[figure not shown]

Figure 1: Schematic representation of the surfaces of a lumpectomy cavity (white circle). The posterior margin is nearest the fascia. The anterior margin (not shown) is nearest the skin.

For each of the lumpectomy surfaces, we use the naming convention shown in **Figure 2** to compare imaging versus pathology. For example, consider the lateral location. The surface of the gross resection facing the lateral location is called margin 1 (M1). The exposed surface in the lateral location of the lumpectomy cavity is called tumor bed 1 (TB1). Once the standard of care cavity shaving specimen is taken, the opposite side of the shaving is called margin 2 (M2). The newly exposed surface in the lumpectomy cavity is called tumor bed 2 (TB2). We use this naming convention throughout this protocol.

[figure not shown]

Figure 2: Schematic representation of the gross resection and the cavity shavings. Standard of care lumpectomy is depicted in blue (lumpectomy specimen and first cavity shaving). The second (yellow) and third (red) cavity shavings are only removed when the LUM Imaging System indicates that residual cancer is present (Phase B of the Feasibility study).

The following will be used as the definitions for determining the performance of the LUM imaging system at the per-tissue level.

- True positive = fluorescence above normal tissue threshold found in the sample + abnormal tissue found in the sample by histopathology
- False positive = fluorescence above normal tissue threshold found in the sample + no abnormal tissue found in the sample by histopathology
- True negative = no fluorescence above normal tissue threshold found in the sample + no abnormal tissue found in the sample by histopathology
- False negative = no fluorescence above normal tissue threshold found in the sample + abnormal tissue found in the sample by histopathology

The Feasibility Trial:

LUMICELL COMPANY CONFIDENTIAL
This document is confidential. Do not disclose or use except as authorized.

Phase A will consist of **15 evaluable subjects**

- Arm 1: 5 subjects not injected with LUM015
- Arm 2: 5 subjects injected with 0.5 mg/kg of LUM015
- Arm 3: 5 subjects injected with 1.0 mg/kg of LUM015

The first group of 5 subjects was not injected with LUM015 to measure the normal tissue autofluorescence baseline. The second group of 5 subjects was injected with LUM015 at a dose of 0.5 mg/kg. The third group of 5 subjects was injected with LUM015 at a dose of 1.0 mg/kg to assess the ability to distinguish LUM015 fluorescence signal from autofluorescence baseline. The objective was to determine the average tumor-to-normal tissue signal ratio (T:N) at both the 0.5 mg/kg and 1.0 mg/kg doses. In previous versions of the Investigational Protocol, the dose that generated the highest tumor-to-normal tissue signal ratio was going to be selected for Phase B. If both doses generated the same T:N, then the lowest dose, namely 0.5 mg/kg, was going to be selected for Phase B.

Based on Phase A data, Lumicell developed a dose-response model (see Appendix C) to predict the effects of dose on T:N and signal variations. Based on these results, the dose of 1.0 mg/kg was selected for Phase B.

Subjects in Phase B will be injected with a dose of 1.0 mg/kg. Phase B will enroll **10 evaluable subjects** with positive margins based on histological margin assessment from the initial shaved margin (with a **maximum enrollment of up to 50 subjects to achieve 10 subjects with positive margins**).

The total enrollment of the Feasibility study is 25 to 65 subjects (15 subjects in Phase A and up to 50 subjects in Phase B). The endpoints for the Phase A and Phase B of the Feasibility study are outlined below.

Endpoints:

Phase A:

- Select the dose (either 0.5 mg/kg or 1.0 mg/kg) for Phase B and pivotal studies that generates the largest average tumor-to-normal tissue signal ratio.
- Define the parameters for the detection algorithm to be used in the Phase B portion of the study.
- Collect safety data

Phase B:

- Evaluate and, if necessary, adjust the detection algorithm parameters
- Adjust, if necessary, the protocol for the pivotal trial.
- Collect safety data

LUMICELL COMPANY CONFIDENTIAL

This document is confidential. Do not disclose or use except as authorized.

General Procedure: (Same for both Phase A and B)

The first group of 5 subjects in Phase A will not be injected with LUM015 but will undergo the procedure outlined below as if they were injected with LUM015. Because of their exposure to the LUM 2.6 Imaging Device, these initial 5 subjects will be followed and monitored for safety in the same manner as all the patients injected with LUM015. The second group of 5 subjects (and the third group of 5 subjects, if necessary) in Phase A and all subjects in Phase B will be injected with LUM015 between 2 to 6 hours prior to surgery at a dose of 0.5 mg/kg, or 1.0 mg/kg. The selection of these doses and the timing of injection prior to surgery are based on the results of an IND phase I study in sarcoma and breast cancer subjects undergoing tumor removal surgery. A summary of the IND phase 1 study can be found in Section 10 below. Subjects will be observed to collect safety data of the LUM Imaging System from the time of injection of LUM015 to the time they are discharged from the hospital. The subjects will have a final safety assessment at the first post-operative visit.

Patients will be injected with LUM015 2-6 hours prior to surgery. For patients with non-palpable tumors, an ultrasound or mammogram guided needle localization procedure will be performed after LUM015 injection. Patients having sentinel node biopsies will be injected with Technetium-99 per standard of care. The injection of Technetium-99 may occur before or after injection of LUM015. Note that methylene blue or any other blue dye used for sentinel node mapping will not be used in this study.

Prior to the surgery, the LUM 2.6 Imaging Device will be located in the surgery room and an initialization procedure will be conducted to ensure that the performance parameters of the device are within defined specifications. If during the initialization procedures, the performance parameters are outside the defined specification, the user is prompted to discontinue use of the device. These patients will receive standard of care treatment and will not be imaged with the LUM 2.6 Imaging Device. These patients will be followed and monitored for safety the same way as those patients that undergo imaging with the LUM 2.6 Device. These patients will be included in the safety cohort but will not be part of the imaging analysis (efficacy) cohorts.

During histology analysis by the pathologist, images from the histology slides will be recorded for concordance with the fluorescence imaging results from the LUM 2.6 Imaging Device.

Phase A Procedures:

1. LUM 2.6 Imaging Device is initialized.
2. For surgeries with sentinel lymph node resection:
 - a. surgeon performs axillary incision
 - b. surgeon records 3-4 images of normal appearing tissue within the axillary incision using the LUM 2.6 Imaging Device
 - c. surgeon performs sentinel node resection procedures and sends node specimen for intraoperative analysis

LUMICELL COMPANY CONFIDENTIAL

This document is confidential. Do not disclose or use except as authorized.

- d. surgeon records whether any interference or adverse impact of LUM015 on the sentinel lymph node procedures.
3. Surgeon performs surgical incision in the breast.
4. Surgeon removes lumpectomy specimen (gross resection).
5. For non-palpable tumors, the lumpectomy specimen is imaged by x-ray at the OR suite. The surgeon will remove additional tissue (which is part considered part of the gross resection) if indicated by the x-ray imaging results.
6. Surgeon records 3-4 images of normal appearing tissue on the underside of the skin flaps using the LUM 2.6 Imaging Device. These images will be used for evaluation of baseline fluorescence of normal tissue.
7. Surgeon scans the tumor bed cavity (TB1, **Figure 2**) with the LUM 2.6 Imaging Device and research assistant records images from every surface. The surgeon is blinded to the images.
8. Surgeon removes one shaved margin specimen from each tumor bed cavity surface per standard of care at MGH. Final margin assessment is based on pathology analysis of this shaved margin specimen.
9. Surgeon scans the tumor bed cavity (TB2) with the LUM 2.6 Imaging Device and research assistant records images of every surface. The surgeon is blinded to the images.
10. Standard of care surgery continues.
11. Surgeon or research assistant records images from the 6 faces of the lumpectomy specimen ex vivo using the LUM 2.6 Imaging Device.
12. Surgeon or research assistant records images of both sides of the shaved margin specimens (TB and M surfaces) ex vivo using the LUM 2.6 Imaging Device and marks with purple ink areas highlighted as suspicious by the LUM Device.
13. Surgeon or pathologist inks and then transects the lumpectomy specimen and records an image from the cross section of the specimen.

The table below shows the data to be collected. Note that TB1 will be imaged twice: once in vivo in the lumpectomy cavity and once ex vivo in the shaved margin to account for potential spatial differences between the in vivo and ex vivo tissue images.

Table 1: Imaging and pathology data to be collected in the Feasibility Phase A study.

Location	Lumpectomy specimen (ex vivo)		Lumpectomy cavity TB1 (in vivo)	Shaved cavity margin		Lumpectomy cavity TB2 (in vivo)
	M1	Transection		TB1 (ex vivo)	M2 (ex vivo)	
Anterior	Imaging and pathology (when available)	Imaging and pathology (when available)	Imaging only	Imaging and pathology	Imaging and pathology	Imaging only
Posterior	Imaging and pathology (when available)	Imaging and pathology (when available)	Imaging only	Imaging and pathology	Imaging and pathology	Imaging only

Superior	Imaging and pathology (when available)	Imaging and pathology (when available)	Imaging only	Imaging and pathology	Imaging and pathology	Imaging only
Inferior	Imaging and pathology (when available)	Imaging and pathology (when available)	Imaging only	Imaging and pathology	Imaging and pathology	Imaging only
Medial	Imaging and pathology (when available)	Imaging and pathology (when available)	Imaging only	Imaging and pathology	Imaging and pathology	Imaging only
Lateral	Imaging and pathology (when available)	Imaging and pathology (when available)	Imaging only	Imaging and pathology	Imaging and pathology	Imaging only

Final margin assessment will be done by radial sectioning of the cavity shavings to examine the M2 surface per standard pathology protocols.

Imaging data with their respective histologic assessment for the presence of abnormal tissue were used to generate receiver operator characteristics (ROC) curves based on Luminicell's abnormal tissue detection thresholds described below.

From the Phase A imaging data, Luminicell used the metric of TB1000, which is defined as the minimum signal from the brightest contiguous cluster of 1000 μm diameter in the field of view. We selected the TB1000 metric as it represents true spatial characteristics of foci of cancer and is likely to give the best results going forward. The data from Phase A showed relatively small patient-to-patient variations in signal, thus a fixed, absolute threshold can be used to discriminate between tumor and normal tissue images. The fixed threshold is represented as:

$$\text{Tumor present if } \text{TB1000 signal in a given tissue image} > Y$$

Although our Phase A data shows that a fixed threshold works well with the small population tested, it is possible that with a larger population we may encounter larger patient-to-patient variations. Thus, Luminicell decided to plan for the possibility of needing a threshold that varies proportional to normal tissue signal. This patient-specific variable threshold is represented as:

$$\text{Tumor present if } \text{TB1000 signal in a given tissue image} > a * \text{subject's normal tissue signal baseline}$$

The normal tissue signal baseline is determined by calculating the 25th percentile for each of the in vivo images recorded before the surgeon removed the standard of care cavity shave and selecting the lowest value among them.

Luminicell's software compares the fixed threshold with the patient-specific variable threshold for each patient and will select the lower of the two to determine whether tumor is present in the tissue until one threshold approach proves to be superior.

Phase B Procedures:

1. LUM 2.6 Imaging Device is initialized.
2. For surgeries with sentinel lymph node resection:
 - a. surgeon performs axillary incision
 - b. surgeon records 3-4 images of normal appearing tissue within the axillary incision using the LUM 2.6 Imaging Device
 - c. surgeon performs sentinel node resection procedures and sends node specimen for intraoperative analysis
 - d. surgeon records whether any interference or adverse impact of LUM015 on the sentinel lymph node procedures.
3. Surgeon performs surgical incision in the breast.
4. Surgeon removes lumpectomy specimen (gross resection).
5. For non-palpable tumors, the lumpectomy specimen is imaged by x-ray at the OR suite. The surgeon will remove additional tissue (which is part considered part of the gross resection) if indicated by the x-ray imaging results.
6. Surgeon records 3-4 images of normal appearing tissue on the underside of the skin flaps using the LUM 2.6 Imaging Device. The software will use these images to set the abnormal tissue detection threshold using the algorithm confirmed during Phase A.
7. Surgeon scans the tumor bed cavity (TB1) with the LUM 2.6 Imaging Device and research assistant records images from every surface and takes note of the quadrants identified as containing fluorescence above the abnormal tissue threshold (these regions will be displayed in red in the screen). The surgeon is blinded to the images.
8. Surgeon removes one shaved margin specimen from each tumor bed cavity surface per standard of care at MGH. This shaved margin specimen will be analyzed by the pathologist to evaluate whether the subject had a positive margin after standard of care treatment.
9. Research assistant informs the surgeon of the imaging results from step 4.
10. Surgeon scans the tumor bed cavity (TB2) with the LUM 2.6 Imaging Device while surgeon and research assistant observe the real-time imaging results. Research assistant will record an image from each surface.
11. Surgeon removes an additional shaved margin specimen from any surface showing residual fluorescence (highlighted in red in the screen). Surgeon will repeat the imaging procedure until no residual fluorescence is observed but will not remove more than a total of 2 cm of additional margin tissue in depth. Final margin assessment for each lumpectomy surface is based on pathology analysis of the final shaved margin specimen.
12. Surgeon or research assistant records images from the 6 faces of the lumpectomy specimen ex vivo using the LUM 2.6 Imaging Device and applies purple ink to areas showing fluorescence.

LUMICELL COMPANY CONFIDENTIAL

This document is confidential. Do not disclose or use except as authorized.

13. Surgeon or research assistant records images of both sides of the shaved margin specimens (TB and M surfaces) ex vivo using the LUM 2.6 Imaging Device and applies purple ink to areas of shaved margin specimens showing fluorescence.
14. Surgeon or pathologist inks and then transects lumpectomy specimen and records an image from the cross section of the specimen.
15. Standard pathology inks will be applied by the pathologists per standard of care to gross specimen and shave margin specimen surfaces over the ink marking fluorescence, allowing complete pathological correlation of fluorescence and standard pathology findings.

Imaging data from gross resection dissection, M1, TB1 and M2 with their respective histologic assessment (when available) for the presence of abnormal tissue will be used to preliminarily evaluate the feasibility of the detection algorithm in identifying residual cancer. In addition, data analysis will compare positive margin rates based on the first standard of care shaved cavity margin (M1) and the positive margin rate based on the final, image guided shaved margin. This data will support the endpoints for the subsequent pivotal study.

During Phase B, after every 10 subjects complete the study, the safety data will be reviewed before recruiting the next 10 subjects. After every 10 subjects, we will also evaluate the device functionality based on the initialization procedure results and any changes to correct the device settings/components will be made.

[figure not shown]
In some surgeries when the tumor is near the skin, a thin layer of tissue may be left just under the skin. Preliminary data shows that high fluorescence from the skin may create artifacts when imaging the thin layer of tissue in the lumpectomy cavity. In order to analyze possible artifacts caused by skin's fluorescence, we will perform imaging of the external breast tissue (skin) with the LUM Imaging Device pre and post injection of the LUM015 dye. Our intent is for a physician or research assistant to obtain a baseline signal background measurement by placing the LUM Imaging Device on ipsilateral and contralateral breast skin. Images will be taken prior to injection to within 30 minutes post injection. This data may provide information for developing the patient-specific tumor detection algorithm. If the physician or research assistant deems that this procedure will add additional stress, the external breast imaging will not occur.

Pathology analysis:

[figure not shown]
The purple ink applied during the ex vivo imaging procedures with the LUM 2.6 Imaging Device will not interfere with standard pathology procedures (see Appendix B for a detailed pathology protocol). The purple ink will be applied to both surfaces of the shaved margin, except on the final shaved margin in which the purple ink will be applied only to the TB surface. All the resected specimens will be inked and processed per standard of care pathology procedures. After all the standard of care pathology procedures are completed, the study pathologist will review histopathology of areas marked with purple ink that designate areas of fluorescence identified by the LUM 2.6 Imaging Device and correlate fluorescence with histopathology findings. See Appendix B for details of the pathology procedures.

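### Does the M1 label on the Phase B before/after margin comparison put the baseline on the wrong surface?

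*Combined protocol and SAP*

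**What the plan says.** The nomenclature part of Section 1.1 fixes the labels. On the specimen side: "The surface of the gross resection facing the lateral location is called margin 1 (M1"). On the shave side: "Once the standard of care cavity shaving specimen is taken, the opposite side of the shaving is called margin 2 (M2"). It adds: "We use this naming convention throughout this protocol". Table 1 (Phase A) follows the convention, with M1 under the lumpectomy specimen and TB1 and M2 under the shaved cavity margin.

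The data analysis paragraph at the end of the Phase B Procedures describes the comparison: "data analysis will compare positive margin rates based on the first standard of care shaved cavity margin (M1) and the positive margin rate" from the last image-guided shave. The sentence just before it lists M1, TB1 and M2 as separate surfaces.

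Four other places bear on which specimen carries margin status:

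- Phase B enrolment, Section 1.1: the target is 10 evaluable subjects "with positive margins based on histological margin assessment from the initial shaved margin".
- Phase A Procedures, after Table 1: "Final margin assessment will be done by radial sectioning of the cavity shavings to examine the M2 surface per standard pathology protocols".
- Phase B step 8, on the first shave: "This shaved margin specimen will be analyzed by the pathologist to evaluate whether the subject had a positive margin after standard of care treatment".
- Phase B step 11: "Final margin assessment for each lumpectomy surface is based on pathology analysis of the final shaved margin specimen".

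Section 14.2 also counts positive-margin subjects on the initial shaves. It uses neither label and does not describe the before/after comparison. The comparison is not among the Phase B endpoints in Section 1.1 or Section 14.2.

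**The concern.** Under the protocol's own definitions, a margin rate based on M1 is the rate before the routine shave, and a rate based on M2 is the rate after it. Only the second isolates what the guided shaves add. The comparison sentence attaches M1 to the shave, it is the only place where the comparison is specified, and the statistical section does not correct it.

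The direction of a possible error also matters. If the baseline were taken from the gross resection, any tumour at that surface that the routine shave cleared would count as a reduction due to the imaging system. The paragraph says these data will support the endpoints of the pivotal study, so an inflated reduction could be carried forward. The sentence also leaves open whether the rate is per subject or per surface, and how the paired before/after results are to be handled.

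**Working it through.** **1. Which specimen is meant.** Set the competing readings side by side.

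| Source | Points to |
|---|---|
| Words of the comparison sentence | first routine shave |
| Label in the same sentence | gross resection (M1) |
| Phase B step 8 | first routine shave |
| Phase B enrolment target, Section 1.1 | first routine shave |
| Section 14.2 | first routine shave |
| Phase A text after Table 1 | shave, M2 surface |

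One parenthetical label stands against the sentence's own words and four other places. Section 1.1 defines a positive margin as tumour on the inked surface. For final shaved margins, Appendix B has pathology ink the outer (M) side of the shave. That agrees with M2.

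**2. Stated figure.** Section 14.2 gives a maximum of 50 subjects, from 10 positive-margin subjects at a 20% rate: 10 / 0.20 = 50. This reproduces. The 10 are counted on the initial shave, so correcting the label leaves it at 50.

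**3. What a literal reading would do.** Let F be the final positive-margin rate.

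- Reduction from an M1 baseline: P(M1+) − F
- Reduction from an M2 baseline: P(M2+) − F
- Difference between them: P(M1+) − P(M2+), whatever the value of F

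Take P(M2+) = 20% from Section 14.2. The documents give no P(M1+), so the values below are assumptions.

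| Assumed P(M1+) | Spurious reduction |
|---|---|
| 25% | 25 − 20 = 5 points |
| 30% | 30 − 20 = 10 points |
| 40% | 40 − 20 = 20 points |
| 50% | 50 − 20 = 30 points |

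This is a shift in the baseline over all subjects. It should not be read as a count among those who have no guided shave, because the documents do not say how many those would be. For a subject with no guided shave, step 11 makes the first shave the final specimen, so the shave-based change is exactly 0.

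**4. Unit and pairing.** Section 14 opens with the rate of patients with positive margins, step 8 asks about the subject, and the enrolment target and Section 14.2 count subjects. Each subject supplies both the first-shave result and the final result, so the pairing is in the data.

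**The case for a change.** The strongest case for a change is that M1 and M2 are more than prose. They are the names attached to imaging and pathology records, and someone who pulls the baseline by label would take the wrong surface. The slip would favour the device, and Section 14 states the trial's objective as a reduction in positive margins, which only this comparison measures. With 4 to 6 shaves per subject, a per-surface rate would differ from a per-subject rate. A guided shave can itself be positive, so conversions in both directions are worth reporting. Correcting the label would cost a few words.

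Much of this is true. The inconsistency is real and comes from the protocol, not from the PDF conversion. Section 14.2 does not expressly settle the label, and a tabulation of paired conversions would be good practice.

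The step from a wrong label to a wrong result does not stand. Shave-based status must already be determined for every Phase B subject in order to count towards the 10 positives, so the correct baseline is at hand under the plan's own rules. M1 pathology is listed in Table 1 only when available, a limit that the table does not put on the shave surfaces. (The Phase B paragraph applies that limit to all its surfaces together.) A complete M1 baseline is therefore not assured.

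The missing unit, pairing and intervals are absent detail in a descriptive analysis for which Section 14.1 plans summary tabulations. Specifying intervals would not make it more informative: with 10 shave-positive subjects, the exact 95% interval is 18.7% to 81.3% for 5 converted and 44.4% to 97.5% for 8.

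**Conclusion.** This is a clerical slip and calls for no change to the plan. The comparison sentence means the first routine shave, whose margin surface is M2 under the protocol's convention. A statistician following the document would use it. The correct reading changes no result and no stated figure: the ceiling of 50 stands, and the shave-based change is 0 where no guided shave is taken.

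The 5 to 30 point distortion arises only if the label overrides the sentence's own words, step 8, the enrolment target and Section 14.2, and if the M1-positive rate is 25% to 50% against the planned 20%. The first condition is unlikely, and the second is assumed. The unit and the pairing are left to the analyst, but the text points to the subject and the same subjects supply both rates. The conclusion rests on the comparison remaining additional and descriptive in a feasibility study. A pivotal study that took it as an endpoint would need it fully defined there.
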